9.4 STATISTICAL ANALYSES

9.4.1 GENERAL APPROACH

Statistical analyses will be reported with tables, figures, and listings. Tables and figures will be summarized by treatment group. Tables summarizing demographics and other baseline characteristics will also include a column for all participants combined.

In general, continuous variables will be summarized to indicate the population sample size (N), number of participants with available data (n), mean, SD, median, minimum, and maximum values. Categorical variables will be summarized by the N, n, number of participants in each category, and the percentage of participants in each category. Unless otherwise noted, the denominator to determine the percentage of participants in each category will be based on the number of participants with available data. Select ordinal data may be summarized using both descriptive statistics and counts and percentages of participants in each category, as appropriate.

Statistical significance testing will be 2-sided and performed using alpha=0.05.

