3.5. Escape Medication

For participants with measured myopia progression ≥ 2.00 D from baseline in SE at a visit occurring between Month 18 and Month 36 (inclusive), and measurements obtained 6 months later at the next scheduled visit to confirm myopia progression (ie, confirmation at a visit between Month 24 and Month 42 [inclusive]), then treatment with escape medication (active SYD-101 0.03%) will be initiated at the confirmatory visit and continued until Month 48.

Participants on escape medication will adhere to the same visit schedule. No medications will be dispensed during or after the Month 48/End of Study (EOS) visit. As with masked study treatment, open-label SYD-101 0.03% (escape medication) will be provided by the sponsor, managed and tracked using IVRS/IWRS, and dispensed to participants by the assigned site staff.

4. General Statistical Considerations

All statistical analyses will be conducted using SAS Version 9.4 or higher (SAS Institute, Cary, North Carolina).

All statistical tests will be two-sided and will be performed at the 5% level of significance leading to 95% (2-sided) confidence intervals (CIs), unless otherwise stated. P-values will be rounded to 3 decimal places. If a p-value is less than 0.001 it will be reported as “<0.001.” If a p-value is greater than 0.999 it will be reported as “>0.999.”

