4.1. Sample Size

Group sample sizes of 280 in each treatment arm will achieve at least 90% power to detect a difference in the percentage of participants with myopic progression (>0.75 D) of at least 15% between a SYD-101 arm and Vehicle. Power calculations presented in Figure 4-1 are based on the Chi-squared test at a 2-sided significance level of 0.025.

[figure not shown]
Figure 4-1 Power for 2-Sided Chi-Square Test Evaluated at Alpha=0.025 for Proportion Responders When 280 Participants Per Arm

Additionally, group sample sizes of 280 per treatment arm achieves >90% power to detect a reduction of 0.18 D or more in the annual progression rate between SYD-101 and Vehicle, assuming a common SD of 0.60 D. Power calculations presented in

Figure 4-2 are based on a 2-sample t-test evaluated at the 0.025 significance level.

Figure 4-2 Power for 2-Sided T-Test Evaluated at Alpha=0.025 for Annual Progression Rate When 280 Participants Per Arm

Furthermore, to estimate the statistical power of the two region- specific primary endpoints, simulations based on various assumptions regarding the mean vehicle annual progression rate, the mean active annual progression rate based on % reduction from the vehicle annual progression rate, the SD for the APR as well as allowing for participant dropout/study treatment discontinuation and escape medication have been considered to investigate statistical power for a range of sample sizes. Simulations were run after the protocol was finalized to assess protocol sample size assumptions. For the most likely assumption of parameters examined, a mean placebo/control APR of 0.65 D and a mean active APR 0.325 D (a 50% reduction from the mean vehicle/control APR) both with a SD of 0.55 D and an annual dropout/study treatment discontinuation rate of 7%, a sample size of 217 participants per treatment arm provides an approximate 97% power for the FDA endpoint and an approximate 99.96% power for the EMA endpoint assuming a significant level of 0.025.

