Prior to the Month 24 database lock, all study team members at PPD, Santen, and Sydnexis will be masked to the treatment assignments, with the exception of the PPD randomization, IRT, and Clinical Supplies teams as their roles require access to the randomization and materials schedules.

Following the 24-Month database lock, PPD will send the study data and randomization code to Santen team members who will be responsible for running the statistical programs and producing the tables, listings, and graphs for the CSR. The data will be subset so that only observations through the Month 24 timepoint are included and only the initial randomization assignments will be provided. An independent medical writer will prepare the CSR and clinical modules of the MAA under Santen's supervision. Sydnexis will appoint a designee to review and approve the CSR who will not have day-to-day contact with any study sites. Santen team members will be unmasked and will not have any contact with study sites.

After the Month 36 database lock, the PPD Project Manager, PPD Oversight Director and the PPD Biostatistics and Programming team members as well as Sydnexis designees will become unmasked at the participant-level. Only the initial treatment assignments will be unmasked. The re-randomization of subjects at Month 36 will remain masked until the Month 48 database lock. The PPD Clinical team members responsible for monitoring participant data (Clinical Research Associates/Clinical Trial Managers), the PPD Medical Monitor, and Data Management team members, will remain masked to participant-level treatment assignments until after the Month 48 database lock. PPD will maintain separate access-controlled areas for the generation and distribution of the unmasked Month 36 analyses and will document team members who have access to these areas in the TMF.

Additionally, to minimize bias, results of the Month 24 analyses for EU submission will neither be made public, nor shared with study sites nor study monitors until after-Month 36 database lock; participant treatment assignments will remain masked until after the Month 48-lock. A masking plan will detail the names and roles of persons who will have access to the Month 24 and Month 36 aggregate data and participant treatment assignments.

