For all statistical tests, unless otherwise stated, a two-sided type I error rate of 5% will be used, with corresponding 95% CIs and associated p-values provided as appropriate.

All efficacy endpoints will be summarized by treatment group and visit per the reporting conventions described in Section 4. Individual participant listings for each efficacy endpoint will be provided to support the summary tables.

Note: In the event that a site is identified as having significant improper investigator oversight, the primary and secondary efficacy analyses will be performed both with and without this site's data to assess its significance.

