The proportion of participants with confirmed myopia progression (>0.75 D) at Month 36 will be compared between each dose of SYD-101 and Vehicle using pairwise CMH tests to account for randomization factors (ie, baseline SE and age categories). The pairwise CMH tests will be performed and the Mantel-Haenszel common risk difference 95% CIs will be calculated for each of the k imputed datasets and the results combined via SAS PROC MIANALYZE for final treatment estimates. Point estimates and CIs will be presented in summary tables as percentages (i.e., the estimated proportions * 100).

Rubin's pooling methodology utilized in SAS PROC MIANALYZE is based on assumption that the estimates are asymptotically normally distributed. The CMH test follows a Chi-Square distribution which is highly skewed for smaller degrees of freedom and can violate Rubin's assumptions. Prior to combination of data in the MIANALYZE procedure, the individual CMH test statistics will be transformed to an approximate Normal (0,1) variables using the Wilson-Hilferty transformation ([Wilson & Hilferty, 1931](#); [Goria, 1992](#)).

The number and percentage of participants in each treatment group who meet the definition of myopic progression will be presented. These values will be based on the averages from the k imputations.

The same analysis will also be performed at Month 24 looking at progression at or before Month 24 as a secondary analysis.

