 - If Endpoint 6 (or Endpoint 7) is not statistically significant, then all subsequent endpoint(s) will be considered descriptive/nominal.

For the EMA submission, the key secondary endpoint will be the proportion of participants with myopic progression >0.75 D at or before Month 24. The analysis will use the same methodology as stated in Section **Error! Reference source not found..**

For the FDA submission, the key secondary endpoint will be the mean annual progression rate of myopia using data through Month 36. The analysis will use the same methodology as specified for this endpoint in Section **Error! Reference source not found..**

All other secondary endpoints will be analyzed at both Month 24 and Month 36 except for the Fast Progressor Subgroup 1 and Subgroup 2 analyses for the EU submission which is analyzed at Month 24. For Fast Progressor Subgroups 1 and 2, data after receipt of prohibited treatment or escape medication will be censored and multiple imputation will not be performed for this endpoint. The censoring and MMRM analysis methods will be utilized for study discontinuation (regardless of reason) and receipt of prohibited treatment or escape medication. The analyses at Month 24 will be considered the primary timepoint for assessment of secondary endpoints for the EMA submission with analyses generated at Month 36 being considered exploratory.

Conversely, the analyses at Month 36 will be considered the primary timepoint for assessment of secondary endpoints for the FDA submission, and the results generated at Month 24 being considered exploratory.

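### Does the FDA primary test need a written rule for turning the pooled Wilson-Hilferty CMH statistic into a p-value?

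*SAP*

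**What the plan says.** SAP 8.1.1 (FDA part) and Protocol 9.4.2 run a pairwise stratified CMH test in each imputed data set. Then "the individual CMH test statistics will be transformed to an approximate Normal (0,1) variables using the Wilson-Hilferty transformation", and the values are combined in PROC MIANALYZE. SAP 8.1.1 also pools the Mantel-Haenszel risk difference. The resulting p-value is compared with 0.045 or 0.025 (SAP 8.1), or with 0.005 further down the hierarchy when only one dose has succeeded (SAP 8.2).

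Sidedness is covered only in general terms:

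- Protocol 9.4.1: "Statistical significance testing will be 2-sided and performed using alpha=0.05".
- SAP Section 4: tests are "two-sided and will be performed at the 5% level of significance leading to 95% (2-sided) confidence intervals (CIs), unless otherwise stated".
- SAP Section 8, opening text: "unless otherwise stated, a two-sided type I error rate of 5% will be used, with corresponding 95% CIs and associated p-values".
- SAP 4.1: the power calculations for the proportion "are based on the Chi-squared test at a 2-sided significance level of 0.025".

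The same test is used beyond the FDA primary. For the EMA, "the key secondary endpoint will be the proportion of participants with myopic progression >0.75 D at or before Month 24", and SAP 8.2 applies CMH tests to the other progression proportions. SAP 4.2 divides the work: after the Month 24 lock "PPD will send the study data and randomization code to Santen team members who will be responsible for running the statistical programs", and later "PPD will maintain separate access-controlled areas for the generation and distribution of the unmasked Month 36 analyses".

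**The concern.** The text describes the pooled quantity as approximately standard normal, and two-sided testing of a normal value usually means both tails. But this value comes from a chi-square statistic, in which a large effect in either direction gives a large positive value. Taking both tails would count two-sidedness twice and double the p-value.

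This step produces the FDA primary p-value, the EMA key secondary p-value and those of the other CMH-based endpoints. The partner company runs the Month 24 programs and the CRO generates the Month 36 analyses, so the method could be coded differently in the two submissions. A result lying between the two cut-offs would then depend on an unwritten choice, made once the data were unmasked.

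**Working it through.** **Inputs from the plan.** 280 per arm; 15-point difference; at least 90% power at two-sided 0.025 (SAP 4.1); alpha 0.05 and truncation parameter 0.80 (SAP 8.1); 50 imputations (SAP 8.1.1); about 97% power for the FDA endpoint with 217 per arm in the most likely scenario (SAP 4.1).

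**Thresholds reproduced.** 0.05 × 1.8/2 = 0.045; 0.05/2 = 0.025; 0.05 × 0.2/2 = 0.005.

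**Transformation.** For 1 df, z = (X^(1/3) − 7/9)/√(2/9). At X = 0 this is −0.7778/0.4714 = −1.65, the smallest value possible. A two-sided test at 0.05 needs −1.96 in the lower tail, so the lower tail can never reject. Taking both tails therefore only raises the upper bar.

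**Cut-offs and true size.** Solving for X and reading the chi-square(1) tail area (no missing data):

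| Nominal level | Critical X, upper tail | Critical X, both tails | True size, upper | True size, both |
|---|---|---|---|---|
| 0.05 | 3.747 | 4.928 | 0.0529 | 0.0264 |
| 0.045 | 3.922 | 5.113 | 0.0477 | 0.0237 |
| 0.025 | 4.928 | 6.173 | 0.0264 | 0.0130 |
| 0.005 | 7.905 | 9.275 | 0.0049 | 0.0023 |

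A simulation of 2,000,000 null draws gave 0.0262 and 0.0129 at 0.025. The upper tail comes close to the two-sided rate the SAP asks for; both tails give about half of it.

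**Example.** X = 6.0 has chi-square p = 0.0143. The transformed value is z = (1.8171 − 0.7778)/0.4714 = 2.205. Its upper-tail p is 0.0137, which passes 0.025; its two-tailed p is 0.0275, which fails.

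**With between-imputation variance B (assumed; the plan gives none).** The pooled statistic is t = z/√(1 + 1.02B), with df = 49(1 + 1/(1.02B))². For z = 2.205, upper v both tails: B = 0.02, 0.0145 v 0.0291; B = 0.1, 0.0179 v 0.0357; B = 0.3, 0.0270 v 0.0540. The factor of two between the readings does not depend on B.

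**Power for the stated 15-point difference.** Power = Φ((0.15 − c·s0)/s1), where s0 = √(2p̄(1 − p̄)/280) and s1 = √((p1(1 − p1) + p2(1 − p2))/280). The Vehicle rate is not in the text, so rates from 20% to 97.5% were scanned. The lowest power is at 57.5% v 42.5%, where s0 = 0.04226 and s1 = 0.04178.

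- Ordinary chi-square, c = 2.241: Φ(1.32) = 90.7%, which reproduces the plan's figure.
- Upper tail, c = √4.928 = 2.220: Φ(1.34) = 91.1%.
- Both tails, c = √6.173 = 2.484: Φ(1.08) = 85.9%.

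**Power in the SAP's most likely scenario.** 97% at 0.025 implies a shift of 2.241 + 1.881 = 4.12 at 217 per arm. At 280 per arm the shift is 4.12 × √(280/217) = 4.68. Upper tail: Φ(4.68 − 2.22) = 99.3%. Both tails: Φ(4.68 − 2.48) = 98.6%.

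**Which reading the documents support.** The hypotheses in Protocol 9.1.1 and SAP 8.1 have a non-directional alternative. SAP 4.1 calls an ordinary chi-square test two-sided, which is how the upper tail of a chi-square is normally described. SAP Section 8 fixes a type I error rate, and the upper tail approximately delivers it.

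**The case for a change.** The strongest case for a change is that the rule is written nowhere. The programming appendix in SAP 8.1.2 is mentioned for random seeds only. A programmer who reads the normal description together with the blanket two-sided rule could double the p-value in good faith. At 0.025 the two readings part for any X between 4.93 and 6.17, and doubling takes the worst-case power below the 90% the plan claims. One sentence would settle it, and it is better settled before unmasking.

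The arithmetic stands, and so does the omission. Three things limit its weight. First, doubling contradicts the SAP's own error rate and its chi-square power basis, so it is a mistake in applying the plan, not a second legitimate reading of it. Second, the mistake cannot produce a false claim of efficacy; its only cost is the sponsor's power. Third, SAP 4.2 shows one method applied at two time points. It does not say that the code is written independently or that both organisations compute the same p-value. Month 24 is decisive for the EMA and Month 36 for the FDA, with error controlled separately for each (SAP 8.1 and 8.2). Inconsistent coding is possible, but the documents do not show it.

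The upper tail itself runs slightly above nominal at two thresholds (0.0264 at 0.025 and 0.0477 at 0.045). That is approximation error in the transformation at 1 df, and naming the tail would not alter it.

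**Conclusion.** No change to the plan is needed. The SAP leaves out an implementation step whose answer follows from the test it names: the p-value is the upper-tail probability of the pooled transformed statistic, and direction is read from the sign of the pooled Mantel-Haenszel risk difference that SAP 8.1.1 already produces. Followed that way, the test has size 0.0264 at 0.025 and keeps the stated power.

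If someone did double the tail, size would fall to 0.0130. Power would drop by 91.1 − 85.9 = 5.2 points in the worst case for a 15-point difference, and by 99.3 − 98.6 = 0.7 points in the SAP's most likely scenario. These figures assume no missing data, a single comparison at 0.025 and the normal approximation. The worst case is taken over assumed Vehicle rates, and the likely scenario assumes that the test's shift grows with the square root of the sample size.

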8.1.2. Sensitivity Analysis

Sensitivity analysis conducted for primary and key secondary endpoints using a combination of intercurrent event policies. Sensitivity Analysis 6 will be conducted for the confirmed progression > 0.75 D endpoint only, while Sensitivity Analysis 7 will be conducted for the annual progression rate primary endpoint only. Details for each sensitivity analyses are presented below and summarized in Appendix **Error! Reference source not found..**

1. [Sensitivity Analysis 1 \(PPS While on Treatment/Hypothetical\)](#)

For the EMA primary analysis repeated for PPS, intermittent missing data will be considered MAR and multiply imputed. Observations after prohibited medication/treatment or escape therapy will be censored and not imputed. Observations after treatment or study discontinuation due to a related AE will be multiply imputed assuming MNAR. All other observations after treatment or study discontinuation will be multiply imputed assuming MAR. Invalid SE values will be multiply imputed and assumed to be MAR.

For the FDA primary analysis repeated for PPS, intermittent missing data will be considered MAR and will be multiply imputed. Observations after prohibited medication/treatment or escape therapy will be considered non-responders. Observations after treatment or study discontinuation due to a related AE will be imputed as non-responders. All other observations after treatment or study discontinuation will be multiply imputed assuming MAR. Invalid SE values will be multiply imputed and assumed to be MAR.

2. [Sensitivity Analysis 2 \(FAS Treatment Policy for Prohibited Treatment, Escape Therapy and Treatment Discontinuation\)](#)

For the EMA the FAS intermittent missing observation will undergo multiple imputation assuming MAR. Observations after receipt of prohibited treatment, escape therapy or treatment discontinuation will be analyzed as observed. Observations after study discontinuation due to a related AE will be multiply imputed assuming MNAR with a vehicle-based imputation model. All other observations after study discontinuation will be multiply imputed assuming MAR. Invalid SE values will be analyzed as observed.

For the FDA the FAS intermittent missing observation will undergo multiple imputation assuming MAR. Observations after receipt of prohibited treatment, escape therapy or treatment discontinuation will be analyzed as observed. Observations after study discontinuation due to a related AE will be imputed as non-responders. All other observations after study discontinuation will be multiply imputed assuming MAR. Invalid SE values will be analyzed as observed.

3. [Sensitivity Analysis 3 \(FAS MAR Tipping Point\)](#)

Data will first be multiply imputed for the FAS. Intermittent missing observations, observations after receipt of prohibited treatment or escape therapy, and observations after study discontinuation will undergo multiple imputation assuming MAR. For participants that discontinue treatment their observations will be analyzed as observed. Invalid SE values will be analyzed as observed. After imputations are performed, the tipping point method will be performed where a fixed value C is added to each SYD treatment imputed value. A range of values for C will be considered to identify the point at which statistical significance can no longer be claimed for either treatment arm.

4. [Sensitivity Analysis 4 \(FAS MNAR exclude Prohibited and Escape Observations\)](#)

For the FAS intermittent missing observations will undergo multiple imputation assuming MAR. All observations after receipt of prohibited treatment or escape therapy will undergo multiple imputation assuming not at random (MNAR) with a vehicle-based imputation model. For participants that discontinue treatment, their observations will be analyzed as observed. Observations after study discontinuation will undergo multiple imputation assuming MNAR with a vehicle-based imputation model. Invalid SE values will be analyzed as observed.

5. [Sensitivity Analysis 5 \(FAS MNAR include Vehicle post Prohibited and Escape Observations\)](#)

For the FAS intermittent missing observation will undergo multiple imputation assuming MAR. SYD observations after receipt of prohibited treatment or escape therapy will undergo multiple imputation assuming MNAR with a vehicle-based imputation model. For the vehicle group, observations after receipt of prohibited treatment or escape therapy will have observed data included in the MNAR imputation model and used for analysis. For participants that discontinue treatment their observations will be analyzed as observed. Observations after study discontinuation will undergo multiple imputation

assuming MNAR with a vehicle-based imputation model. Invalid SE values will be analyzed as observed.

6. **Sensitivity Analysis 6** (confirmed progression endpoint only – all missing considered progression)

For the FAS and confirmed progression endpoint only, intermittent missing observations will be multiply assuming MAR. Observations after receipt of prohibited medication or escape therapy will be considered MAR and undergo multiple imputation. For participants that discontinue treatment, their observations will be analyzed as observed. If a participant discontinues the study prior to Month 24 or 36 (depending on analysis timepoint) and has not achieved a confirmed progression prior to their study discontinuation, then the participant will be considered a non-responder, regardless of reason for discontinuation. Observations of participants that discontinue treatment or have invalid SE values will be analyzed as observed.

7. **Sensitivity Analysis 7** (annual progression rate endpoint only - MMRM no imputations)

For the FAS and annual progression rate analysis only, multiple imputations will not be performed for missing data. Observations after receipt of prohibited medication or escape therapy will be censored (e.g., set to missing.) Observations of participants that discontinue treatment or have invalid SE values will be analyzed as observed. The MMRM approach treats missing data as MAR.

The same analyses as detailed in section 8.1.1 above will be repeated for each sensitivity approach above.

All imputations will utilize prespecified SET SEEDS that will be identified prior to unmasking at for the Month 24 analysis and documented in a programming appendix.

Data assumed to be missing at random will be imputed via MCMC multichain methods with imputation performed separately for each treatment arm and the imputation model will include terms for age at baseline, baseline SE (average of both eyes), and SE values (average of both eyes) at each visit through the specified analysis timepoint, Month 24 or Month 36 as applicable. For the multiple imputation, it is planned to perform k=50 imputations, however the number of imputations may be increased depending on the amount of missing data.

All imputations for data assumed to be missing not at random will be first imputed via MCMC multichain methods to obtain monotone data as above for MAR imputations. The remaining missing SE values will be imputed via a sequential vehicle-based pattern imputation using regression methods for the schedule SE visits through the analysis timepoint, Month 24 or Month 35, using a model including age at baseline and baseline SE (average of both eyes) followed by sequential visits through M24 or M36, imputed values for those on SYD-101 treatment will be based on the Vehicle group.

Data sets will be sorted by treatment and participant id prior to imputation.

